7.1.5.2. Incomplete Dates

If the onset date of the AE is incomplete and the AE stop date is not prior to the first dosing date of study drug, then the month and year (or year alone if month is not recorded) of onset determine whether an AE is treatment emergent. The event is considered treatment emergent if both of the following 2 criteria are met:

- The AE onset is the same as or after the month and year (or year) of the first dosing date of study drug, and
- The AE onset date is the same as or before the month and year (or year) of the date corresponding to 30 days after the date of the last dose of study drug

An AE with completely missing onset and stop dates, or with the onset date missing and a stop date later than the first dosing date of study drug, will be considered to be treatment emergent. In addition, an AE with the onset date missing and incomplete stop date with the same or later month and year (or year alone if month is not recorded) as the first dosing date of study drug will be considered treatment emergent.

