Events with Missing Onset Day and/or Month

An event is considered TE if all of the following 3 criteria are met:

- a) The month and year (or year) of onset date is the same as or after the month and year (or year) of the first dose of study drug administration, and
- b) The month and year (or year) of the onset date is the same as or before the month and year (or year) of the 30th day after the date of the last dose of study drug administration, and
- c) End date is as follows:
 - i) The (complete) end date is on or after the first dose date, or
 - ii) The month and year (or year) of end date is the same as or after the month and year (or year) of the first dose of study drug, or
 - iii) End date is completely missing

Events with Completely Missing Onset Date

An AE with a completely missing onset date is defined as TEAE if end date meets any of the 3 criteria specified above.

- 10) The precision in reporting numerical values should be as follows:
 - a) Raw measurements will be reported the same as the data captured electronically or on the eCRF for all but hematology and chemistry values.
 - b) SD and SE will be reported to one more significant decimal place than the raw measurement.
 - c) Mean, median, minimum, Q1, Q3, and maximum will be reported to the same number of decimal places of the raw measurements.

Exceptions may be considered; for eg, if more than 4 significant digits are provided for the measurement.

Precision for derived parameters as follows:

Parameters	Decimal Places
BMI	2
PK concentration	2

- 11) Incomplete death dates will be imputed as the maximum of the study drug start dates, study drug end dates, clinic or virtual visit dates (LSTSVDT), laboratory visit dates (LSTLBDT), COVID-19 symptom assessment questionnaire dates plus 1.

- 12) Graded Laboratory Abnormalities Summary

The following labels will be used for laboratory abnormalities listings:

Category	Lab Test Label Used in I-lbtox Listing	Toxicity Direction	Lab Test Label Used in t-lbtox Table
Hematology	Hemoglobin	Decrease	Hemoglobin (Decreased)
	Lymphocytes	Decrease	Lymphocytes (Decreased)
	Neutrophils	Decrease	Neutrophils (Decreased)
	Platelets	Decrease	Platelets (Decreased)
	WBC	Decrease	WBC (Decreased)
Chemistry	Albumin	Decrease	Albumin (Decreased)
	Alkaline Phosphatase	Increase	Alkaline Phosphatase (Increased)
	ALT	Increase	ALT (Increased)
	AST	Increase	AST (Increased)
	Bicarbonate	Decrease	Bicarbonate (Decreased)

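### Appendix 2's end-date test is not limited to incomplete dates, so read literally it flags some AEs that ended before the first dose; it also differs from Section 7.1.5.2 on one boundary date

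*SAP*

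**What the plan says.** **Appendix 2, item 9.** For an AE with the onset day and/or month missing, three conditions must all hold. Conditions (a) and (b) place the onset month or year between that of the first dose and that of the 30th day after the last dose. Condition (c) concerns the end date and is met by any one of three alternatives:

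- (i) a complete end date qualifies when it is not earlier than the day of first dosing
- (ii) the end date is set against the first dose by calendar month, or by year alone: "The month and year (or year) of end date is the same as or after the month and year"
- (iii) an end date that was not recorded at all also qualifies

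For an AE with no onset date at all, the same alternatives are reused: "An AE with a completely missing onset date is defined as TEAE if end date meets any of the 3 criteria specified above".

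**Section 7.1.5.2.** For a partial onset, the month-level comparison of onset is opened by a condition on the stop date: "If the onset date of the AE is incomplete and the AE stop date is not prior to the first dosing date of study drug". For a missing onset, three situations are named as treatment-emergent: the stop date is also missing; the AE is one "with the onset date missing and a stop date later than the first dosing date of study drug"; or the stop date is incomplete and its month and year (or year) are not earlier than those of the first dose. Here the month-level comparison of the stop date is confined to incomplete stop dates.

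**Where the flag is used.** Section 7.1.6.1 keeps a by-participant listing of all AEs that shows whether each is treatment-emergent. Sections 3 and 7.8 drop tables, figures and the protocol-specified safety analyses.

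**The concern.** The main text and the programming specification describe one derivation and should give the same flag for the same record. They differ in two places.

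First, alternative (ii) of condition (c) carries no qualifier. A complete end date earlier in the month of the first dose fails (i) but passes (ii), so the record qualifies. An event that ended before the first dose must also have begun before it, so it cannot meet the onset limb of the definition in Section 7.1.5.1.

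Second, when onset is completely missing, Section 7.1.5.2 uses a strict inequality for the stop date and Appendix 2 a non-strict one. A stop date on the first dosing day is therefore treated differently.

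What is at stake is the correctness of one flag in the AE listing that the SAP retains, and whether two programmers working from the two places would agree on it.

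**Working it through.** The SAP gives no figure to reproduce. The check applies both rules to the same records and compares the flags.

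**Inputs**

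- The rules: Section 7.1.5.2 and Appendix 2, item 9, as described above.
- Illustrative dates (assumed, not from the SAP): first dose 15 June 2024, last dose 19 June 2024. Last dose plus 30 days is 19 July 2024.
- Onset: completely missing; June 2024; 2024 only; May 2024.
- End date: missing; month and year only; year only; and every complete date from 20 May to 30 July 2024.
- Appendix 2 was applied twice: with (ii) open to any end date, as worded, and with (ii) limited to incomplete end dates. For complete end dates, (ii) was taken as a comparison of month and year.

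**One record step by step.** Onset June 2024 with the day missing, complete stop date 14 June.

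- Appendix 2: (a) June is not before June, met. (b) June is not after July, met. (c)(i) 14 June is before 15 June, not met. (c)(ii) June equals June, met. Result: treatment-emergent.
- Section 7.1.5.2: the opening condition requires that "the AE stop date is not prior to the first dosing date of study drug". 14 June is before 15 June, so it fails. Result: not treatment-emergent.

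**End dates on which the two rules differ**

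| Onset | (ii) as worded | (ii) limited to incomplete end dates |
|---|---|---|
| June 2024 | 14 (1 to 14 June) | 0 |
| 2024 only | 14 (1 to 14 June) | 0 |
| May 2024 | 0, because (a) fails | 0 |
| Completely missing | 15 (1 to 15 June) | 1 (15 June) |

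In general, with a first dose on day d of a month, d − 1 pre-dose dates in that month are affected; here 15 − 1 = 14. With a completely missing onset the first dosing day is added: 14 + 1 = 15.

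**Redundancy.** Any complete end date on or after the first dose has a month and year no earlier than the first dose's. It therefore always passes (ii) as worded, and (i) adds nothing.

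**Boundary.** For a partial onset, the two places agree on a stop date equal to the first dosing day: both let it through. The disagreement on 15 June arises only when onset is completely missing, and it remains after (ii) is restricted.

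**Realistic reach.** SAP Appendix 1, footnote a, puts screening within 48 hours of baseline. If AEs are recorded only from screening, about 2 pre-dose days are reachable, fewer if the first dose falls on the 1st or 2nd of a month. In the example these are 13 and 14 June: 2 dates for a partial onset, and 2 + 1 = 3 for a missing onset.

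**The case against.** The best defence is that (c) is plainly meant as three exclusive cases: complete, incomplete and missing end dates. The word complete appears in (i), the bracketed mention of year in (ii) is the SAP's usual phrasing for partial dates, and a wider reading of (ii) would leave (i) with no purpose. Section 7.1.5.2 says outright that its own month-level stop-date test is for incomplete dates. This stands as evidence of intent: a reader might infer that the SAP means to count events that ended before dosing, and it does not support that. But the qualifier is missing from the part of the SAP headed as programming specifications, where literal coding is most likely. The argument from intent also leaves the boundary mismatch untouched.

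On that mismatch, it is fair to say that Section 7.1.5.2 does not declare the boundary case non-emergent. It lists what counts and leaves that case out. The documents show a gap in one place and an inclusion in the other, not two express and opposite statements. Nor does the mismatch extend to partial onset dates.

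It is also fair that every AE is listed whatever its flag, so a wrong flag hides no event.

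**Conclusion.** The point holds as a drafting error with a small effect. As worded, Appendix 2 can flag an AE with partial or missing onset whose complete stop date precedes the first dose within the same calendar month. Section 7.1.5.2 excludes it (partial onset) or does not include it (missing onset). The boundary difference is confined to a completely missing onset with a stop date on the first dosing day.

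Two stronger readings are not supported:

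- A reader might infer that a primary safety result is distorted, since incidence of treatment-emergent AEs by Day 35 is a primary endpoint in Section 1.1. No incidence will be tabulated; only the flag in a listing is affected, and only for AEs with incomplete or missing onset.
- A reader might take the 14 dates in the example as the practical exposure. They are the calendar reach of the wording. With the 48-hour screening window, about 2 days are reachable.

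The 2-day figure assumes that AE collection starts no earlier than screening; the AE row of the schedule is redacted and the protocol is not at hand. The SAP does not give the number of AEs with incomplete onset, so no count of affected records can be stated. Treating a truly incomplete end date in the first-dose month as emergent is common to both places and is not in question.

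**What to change.** 1. In Appendix 2, item 9, reword (c)(ii) to: *end date is incomplete and its month and year (or year) is the same as or after that of the first dose*. Both the partial-onset and the missing-onset rules use (c), so one edit serves both.
2. In Section 7.1.5.2, in the sentence on a missing onset, replace *later than* with *on or after*. This matches Appendix 2 (c)(i) and the condition that Section 7.1.5.2 already applies to partial onset dates.

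In the check above, the first edit removes every partial-onset difference and leaves one missing-onset difference; the second removes that one.

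The cost is a few words in two places and one program condition. If the SAP is already final, Section 1 provides for recording the change in the clinical study report.
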